#### 4.3.3. Adverse effects assessment

All participants will be kept for observation for at least 3 hours following each morning treatment for any acute adverse events and additionally will be interviewed and examined about existing and emerging clinical symptoms (i.e. headache, abdominal pain, itching, nausea, vomiting, diarrhea, body temperature, and allergic reaction) before treatment (baseline examination), 3 hours, 24 hours and 28 days after treatment (adverse effects assessment) to determine the occurrence of AE (see chapter 6.2). Any symptoms will be recorded in the CRF and immediate action will be perused (see chapter 6).

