The clinical significant adverse advents of moxidectin are though very similar to those of ivermectin and a consequence of excessive concentration. The drug is typically used as a single oral dose (8 mg) in patients aged 12 years and older and evaluated as an extremely safe drug. Most common side effects include hypotension, itching, headache, abdominal pain, fever, dizziness or diarrhea. Serious or even fatal encephalopathy may occur in patients coinfected with Loa Loa. Furthermore, moxidectin is known to worsen onchodermatitis in patients with hyperactive onchodermatitits. Laos and Cambodia are not endemic neither for Loa Loa nor onchodermatitits and thus these symptomatic advents shall not constitute a risk in our study. Nevertheless patients with symptoms for onchodermatitits (severe itching, bumps under the skin, blindness) will be excluded from the study. Additionally, although conclusive teratogenic data on moxidectin are missing, decreased fetal survival and increased fetal born with malfunctions is observed in some animals studies. Thus we do not see it recommended using moxidectin with pregnant female and pregnant patients will strictly be excluded. Last, owing to the lipophilic nature of moxidectin, extraction of moxidectin to the breast milk of nursing mothers is very likely and could be demonstrated in lactating cows. The risk of moxidectin in nursing infants is though unknown. Breastfeeding females will be excluded in this study.

In a small exploratory study using the veterinary formulation, a single dose of 8 mg of moxidectin, and a small sample size (127 participants) moxidectin has been found to be efficacious against *S. stercoralis* (cure rates of 93.7%) and its tolerability confirmed also in patients [15].

Yet, despite the attractive attributes of moxidectin and its promising potential in the treatment of *S. stercoralis* it remains off-label. First of all, the efficacy of the human formulation against *S. stercoralis* infections has not been assessed to date, neither has the optimal dosage been elucidated. A single dose of 36 mg moxidectin in healthy adults was the highest single dose tested to date that still represented a well-tolerated dose [13]. The 12 mg, therefore, selected as the highest dose in our study to elaborate a dose-response relationship for the use of moxidectin in *S. stercoralis* infections will not pose any health risk.

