#### 4.3.2. Physical and clinical examination

At baseline, the medical history of *S. stercoralis*-infected participants in the study will be assessed with a clinical and physical examination carried out by the study clinician, who will assess weight, height, body temperature, pulse rate, blood pressure. Hemoglobin (Hb) levels will be detected using HemoCue to exclude severely anemic participants (below 80 g/l in adults according WHO) [31]. To avoid accidental treatment of pregnant women all female participants will be asked to provide a urine sample of at least 10 ml to be subjected to a pregnancy RDT. Women will be individually counselled that they should not become pregnant during the entire study period and will be interviewed if they are currently breastfeeding or planning to become pregnant. Any symptoms and abnormalities prior to treatment will be recorded on the case report form (CRF).

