## 4.6. Schedule of visits

Table 1. Schedule of visits of DF (trial A) and parallel group (trial B) study.

Screening /					Follow up		
Time point	Day -28	Day -1-3	0 h	л	3 h	24 h	Day 28
Informed consent	х			ando			
Diagnosis (stool examination) (a)	х			Randomization			х
Questionnaire	х			on and			
Medical history (c)		х					
Clinical examination (d)		Х		ninistr			
Physical examination (e)		х		administration of			
Randomization administration of treatment			х				
Capturing AEs (f)				treatment	х	Х	х
Capturing SAE (f)				1t	х	х	х

(a) on three stool samples duplicate Baermann assays and on two stool samples duplicate Kato-Katz thick smears. (b) date of birth, age, sex, height, weight, body temperature, pulse rate, blood pressure, hb measurement, pregnancy test and recording of breastfeeding

(c) information gained by asking specific questions concerning chronic disease and concomitant medication.

(d) investigation for signs of disease: head ache, abdominal pain, nausea, vomiting, diarrhea, itching, other symptoms. (e) examination on ear, nose, throat, eyes, lungs, lymph nodes and skin.

(f) a standardized symptom questionnaire is used, that includes the recording of headache, abdominal pain, itching, nausea, vomiting, diarrhea, allergic reaction, others

(g) only in trial B

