# 6. Assessment of safety

### 6.1. Adverse event definition

Few adverse events have been reported following moxidectin or ivermectin administration in STH-infected individuals. The most common AEs were abdominal cramps, headache, nausea, diarrhea, fever and vertigo [11, 12, 36, 37].

The observation time for AE starts when the treatment is initiated. Subjects will be kept for observation for at least 3 hours following treatment for any acute AEs. If there is any abnormal finding, the local study physician will perform a full clinical examination and findings will be recorded. An emergency kit will be available on site to treat any medical conditions that warrant urgent medical intervention. Participants will also be interviewed 3, 24 hours, 28 days after treatment about the occurrence of AEs.

Information on all AE (incidence, onset, cessation, duration, intensity, frequency, seriousness and causality) will be entered immediately in the source document, and also in the appropriate AE module of the case report form. For all AEs, sufficient information will be pursued and/or obtained so as to permit i) an adequate determination of the outcome of the event (i.e. whether the event should be classified as a SAE); and; ii) an assessment of the casual relationship between the AE and the study treatments. Intensity of AE will be judged by the study physician, following guidelines by the European Medicine Agency (Note for Guidance on Clinical Safety Data Management).

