#### 6.2. Methods of recording and assessing adverse events

Patients will be kept for observation for at least 3 hours following each morning treatment for any acute AEs. During the reporting period, any unfavorable changes in the subject's condition will be recorded as adverse events, whether reported by the subject or observed by the investigator. In case of any abnormal finding, the local study physician will perform a full clinical examination and findings will be recorded. An emergency kit will be available on site to treat any medical conditions that warrant urgent medical intervention.

In addition, patients will be also interviewed by a nurse and/or a physician about the occurrence of AEs 24 hours after treatment.

Information on all AEs (onset, duration, intensity, seriousness and causality) will be immediately entered in the appropriate AE module of the CRF which is considered as a source document. For all AEs, sufficient information will be pursued and/or obtained so as to permit i) an adequate determination of the seriousness of the event (i.e. whether the event should be classified as a SAE); ii) an assessment of the casual relationship between the AE and the study treatments (i.e. whether the event should be classified as an adverse drug reaction); and iii) an assessment of intensity of AEs by the study physician.

All SAE, unexpected adverse drug reactions, or SUSARs must be reported as described in Section 6.3.

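### Dizziness/vertigo, which the protocol lists among the most common effects, is not a prompted item in the adverse-event questionnaire and may be under-recorded; no post-dose blood pressure reading is stated either.

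*Combined protocol and SAP*

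**What the plan says.** **Expected effects.** The background (section 2) says of moxidectin: "Most common side effects include hypotension, itching, headache, abdominal pain, fever, dizziness or diarrhea". The safety section (6.1), on moxidectin or ivermectin in people with soil-transmitted helminths, says: "The most common AEs were abdominal cramps, headache, nausea, diarrhea, fever and vertigo".

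**What is asked.** Section 4.3.3 has participants interviewed and examined before treatment and at 3 hours, 24 hours and 28 days. The symptoms, introduced by 'i.e.', are "headache, abdominal pain, itching, nausea, vomiting, diarrhea, body temperature, and allergic reaction". Table 1 footnote (f) describes a standardised questionnaire that "includes the recording of headache, abdominal pain, itching, nausea, vomiting, diarrhea, allergic reaction, others". Footnote (d), for the baseline clinical examination, gives a similar list and also ends with an open category.

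**Blood pressure.** Section 4.3.2 places it in the baseline examination by the study clinician, "who will assess weight, height, body temperature, pulse rate, blood pressure". Table 1 footnote (b) groups it with other entry checks: "body temperature, pulse rate, blood pressure, hb measurement, pregnancy test and recording of breastfeeding". No section states a reading after dosing.

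**Other routes of capture.** Section 6.2 provides that any unfavourable change in the subject's "condition will be recorded as adverse events, whether reported by the subject or observed by the investigator". An abnormal finding leads to a full clinical examination.

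**Use of the data.** Safety and tolerability are secondary objectives in both trials. Section 7.3 analyses adverse events descriptively, comparing the proportions reporting them before and after treatment.

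**The concern.** A symptom that every participant is asked about by name and a symptom that has to be volunteered or noticed are not ascertained alike. If the protocol expects dizziness or vertigo to be common and does not prompt for it, its recorded frequency is not on the same footing as that of headache or itching, which are prompted.

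This bears on two uses of the data. Section 4.3 describes the optimal dose as one that balances efficacy against safety concerns and adverse events, so trial A's record of listed effects across 2 to 12 mg feeds the dose choice. Trial B has a comparative safety objective against ivermectin. There is no data and safety monitoring board (section 11.2), so these assessments are the main source of safety information.

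Hypotension raises a related but separate issue. It is a measured sign, and a fall in blood pressure without symptoms would not prompt a report or trigger an examination.

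**Working it through.** The check is mainly a comparison of text. No sample size or error rate in the plan depends on it.

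**Step 1: the seven effects in section 2 against the two solicited lists.**

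| Effect (section 2) | Section 4.3.3 | Table 1 footnote (f) |
|---|---|---|
| Hypotension | no | no |
| Itching | yes | yes |
| Headache | yes | yes |
| Abdominal pain | yes | yes |
| Fever | as body temperature | not named |
| Dizziness | no | no |
| Diarrhea | yes | yes |

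Section 4.3.3 covers 5 of 7 and footnote (f) names 4 of 7. Of the six effects in section 6.1, section 4.3.3 covers five (cramps as abdominal pain, fever as body temperature) and omits vertigo. Footnote (f) names four and omits fever and vertigo. Dizziness and vertigo are counted here as one missing item.

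**Step 2: the two lists against each other.** Body temperature is only in section 4.3.3. The open category is only in footnote (f). Section 4.3.3 reads as a complete list because of 'i.e.', while footnote (f) uses 'includes' and so does not.

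**Step 3: blood pressure.** Section 4.3.2 states it at baseline. Footnote (b) gives no timing, and its marker is attached to no visible row of Table 1, so the table cannot settle when it is measured. The accurate statement is that no post-dose reading is stated.

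**Step 4: the planned analysis.** A before/after comparison needs the same ascertainment on both sides. For blood pressure there is a stated value before treatment and none after. For dizziness both sides rely on unprompted reports, since footnotes (d) and (f) both omit it.

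**Step 5: illustration of size.** Let p be the true rate of dizziness/vertigo and c the share of cases recorded when it is not prompted. Both are assumptions, because the documents give neither.

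- Expected recorded cases in a trial B arm: 175 × p × c.
- Chance of at least one recorded case in a trial A arm of 30: 1 − (1 − p × c)^30.

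| p | c | Expected cases, arm of 175 | Chance of ≥1 case, arm of 30 |
|---|---|---|---|
| 5% | 100% | 8.8 | 0.785 |
| 5% | 50% | 4.4 | 0.532 |
| 5% | 25% | 2.2 | 0.314 |
| 10% | 100% | 17.5 | 0.958 |
| 10% | 50% | 8.8 | 0.785 |
| 10% | 25% | 4.4 | 0.532 |
| 20% | 100% | 35.0 | 0.999 |
| 20% | 50% | 17.5 | 0.958 |
| 20% | 25% | 8.8 | 0.785 |

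**Step 6: effect on comparisons.** If c is the same in two arms with true rates p1 and p2, the recorded ratio is (c × p1)/(c × p2) = p1/p2, which is unchanged. The recorded difference is c × (p1 − p2), which shrinks. The comparison survives but rests on fewer events.

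**The case against.** The strongest reply is that the plan does capture these events. Footnote (f) has an open category, section 4.3.3 says that symptoms of any kind go into the case report form, participants are observed for at least 3 hours, and section 6.2 records reported and observed changes. This stands. A reader might infer that the safety objectives miss dizziness altogether, or that the trials cannot compare it between arms. The documents do not support either reading. The same questionnaire is used in every arm and participants are blinded in both trials, so under-capture should be broadly similar across arms. Its cost is precision.

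Three further limits also stand.

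- Hypotension is in the general drug description in section 2 but not in section 6.1's list for helminth-infected people, so the case for measuring it is weaker than for dizziness/vertigo.
- A reader might link the gap to the lower neurotoxic potential claimed for moxidectin in section 2. That statement cites a study in mice, by its title, and no objective or endpoint concerns neurotoxicity.
- A reader might infer that participants with low blood pressure go home unnoticed. The text shows only that no reading is stated. It does not show what the observation period would find.

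The case report form is not among the documents and may already contain these items. If it does, section 4.3.3 and Table 1 should say so; the two lists need reconciling in any case.

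The objection does not remove the difference between prompted and unprompted symptoms, or the mismatch between the protocol's own list of common effects and its own questionnaire.

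**Conclusion.** The point holds as a modest, inexpensive improvement. Dizziness/vertigo is listed among the most common effects in two sections and prompted for in none. It may therefore be under-recorded relative to the prompted symptoms, which reduces the precision of the dose comparison in trial A and the drug comparison in trial B but prevents neither. The loss cannot be fixed from the documents. Under the assumed ranges (true rate 5% to 20%, unprompted capture 25% or 50%), recorded cases in a 175-participant arm would be a quarter to a half of the true number.

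For hypotension, the descriptive before/after comparison has no systematic post-dose value. This is a secondary matter.

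The conclusion assumes that unprompted capture is incomplete and broadly equal across arms. In trial A the stated blinding covers participants and laboratory technicians, so equal capture of events observed by other staff is itself an assumption there. No efficacy result, sample size or primary analysis is affected.

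**What to change.** 1. Add dizziness/vertigo as one prompted item in section 4.3.3 and in Table 1 footnotes (d) and (f), asked at baseline, 3 h, 24 h and day 28.
2. Make the lists in section 4.3.3 and Table 1 agree with each other, including body temperature and the open category, and reconcile both with the expected effects in sections 2 and 6.1.
3. In section 7.3, state that the item is tabulated by dose arm (trial A) and by treatment (trial B).
4. As a secondary suggestion, record blood pressure at the existing 3 h and 24 h assessments for descriptive tabulation only. No threshold or clinical action is proposed.

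Cost: one added questionnaire item and, if the readings are adopted, some staff time at visits that already take place. Blood pressure is already measured at baseline, and no new visit is needed. If either trial has already collected its data, its report should state that dizziness/vertigo was recorded without prompting.

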#### 4.3.4. Assessment of efficacy after treatment

The efficacy of the treatment will be determined 28 days post-treatment by collecting another three stool samples, which will be microscopically examined for *S. stercoralis* applying each duplicate Baermann technique as well as for potential co-infection with *A. lumbricoides*, *T. trichiura* and hookworm eggs using each duplicate Kato-Katz thick smears on two stool samples.

Participants will be considered *S. stercoralis* cured if no larvae have been found in any of the stool samples. Infection was calculated as larvae per gram stool. LPG will be assessed by calculating the mean of the larvae counts from the three duplicate Baermann assays and adjusted to the previously weighted used amount of stool sample. At the end of the study (day 21) all participants remaining positive for *S. stercoralis* will be treated with ivermectin (200  $\mu$ g/kg), the current standard drug against *S. stercoralis* [9].

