Measurements & procedures	Three stool samples will be collected at baseline if possible on three consecutive days or otherwise within a total maximum of 6 days and analysed by a quantitative Baermann method (in duplicates) for S. stercoralis infection. Co-infection with T. trichiura, A. lumbricoides and hookworm infection will be identified using duplicate Kato-Katz thick smears on stool samples from two consecutive days. The medical history of the participants will be assessed with a standardized questionnaire, in addition to a clinical and physical examination carried out by the study physician shortly before treatment day. The adults will also be interviewed before treatment, 3 and 24 hours as well as 28 days after treatment about the occurrence of AEs. The efficacy of the treatment will be determined 21-28 days post-treatment by collecting another three stool samples. All stool samples will be examined with duplicate Baermann assays and Kato-Katz thick smears and recorded quantitatively. A subsample of adults will further be sampled using finger pricking for micro sampling at 0, 2, 4, 8, 24, and 72 hours, 7 and 28 days post treatment to evaluate pharmacokinetic parameters (trial A). For validation of the analytical method the subsample of one study arm (8 mg, trial A) will undergo venous blood sampling in addition to finger pricking. To all participating households, a brief questionnaire will be administered assessing information on socioeconomic characteristics (possession of indicator assets) and access to sanitation, water facilities, and hygiene behaviour at first visit. Additionally, soil and water samples at different sites will be taken.
Statistical Analyses	An available case analysis (full analysis set according to the intention to treat principle) will be performed, including all subjects with primary end point data. Supplementary, a per-protocol analysis will be conducted. CRs will be calculated as the percentage of larvae-positive subjects at baseline who become larvae-negative after treatment. Larvae per gram (LPG) stool sample will be assessed by calculating the mean of the larvae counts from the three duplicate Baermann assays and divided by the mean weighted amount of these stool samples. The LRR will

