#### 4.3.1. Baseline larval count

At baseline, all participants will be asked to provide three stool samples (if possible on three consecutive days or otherwise within a total maximum of 6 days) [23, 24]. The stool samples Page **18** of **45** 

will be collected until a total of 210 and 350 *S. stercoralis*-infected adults are registered (two out of three stool samples show more than 0.4 LPG (trial A) or 0.1 LPG (trial B), in 10 g of stool sampled per person and time point) in the two studies, respectively. As diagnosing very low-intensity chronic infections remains a major challenge for quantitative and qualitative analysis for *S. stercoralis* only low/moderate to high infection patients are included in trial A (LPG >0.4 on two out of three samples). This inclusion criterion has been shown to result in a diagnostic sensitivity of more than 97% to close to 100%. [24].

Firstly, a quantitative Baermann funnel concentration technique will be used for the quantitative assessment of *Strongyloides stercoralis* infections [24-26] using stool samples from three different (optimal consecutive) days. 5 g stool sample (the stool container with the sample will be weighted before and after the Baermann test was set up) will be placed on gauze inserted into a glass funnel and covered with preheated water to 36°C. Following two hours of artificial light exposure, the collected liquid will be centrifuged and the sediment prepared for analysis by microscope. Duplicate Baermann will be prepared from each stool sample [27, 28]. Secondly, from two stool samples from each participant a duplicate Kato-Katz thick smear will be prepared to detect co-infection with any of the three major soil-transmitted helminthic infections (STHs), namely *Ascaris lumbricoides, Trichuris trichiura* and the hookworms (*Necator americanus* and *Ancylostoma duodenale*) [29]. If additional coinfections are observed, they will be assessed likewise.

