#### 4.4. Measure to minimize bias

Study participants eligible for treatment will be randomly assigned to one of the seven treatment arms (trial A: DF study) or to one of the two treatment arms (trial B: parallel group study) using a computer-generated stratified by 3 levels of baseline infection intensity (light  $\geq$ 0.4 (trial A) or 0.1 (trial B) – 1 LPG, moderate >1-10 LPG and heavy >10 LPG), block randomization code. The random allocation sequence with varying random blocks of 7 or 14 (trial A) and 2 or 4 (trial B) will be provided by a statistician not involved in enrolment, treatment, and data collection. Stratification will guarantee similar proportion of participants with different infection intensities in all treatment arms. The number of light vs moderate vs. heavy infections, however, are not expected to be equal in each arm, depending on the distribution of infection intensity in the recruited cohort. The codes will be held in a locked cabinet at the Swiss Tropical and Public Health Institute. A copy of this code will be kept in a sealed envelope by one of the co-investigators (will only be opened in emergency situations, determined by the principal investigator upon consultation with the co-investigators). The blinding will be maintained throughout the trial until data entry and processing are complete and the data have been verified. Following release of the final data, the randomization codes will be released.

In previous studies [36] we have observed moderate cure and larvae reduction rates in placebo treated children which are in most cases likely due to the imperfect sensitivity of anthelminthic diagnostics. Participants treated with placebo will be treated at follow up (4 post treatment) with ivermectin (200  $\mu$ g/kg). This treatment delay does not cause noteworthy harm.

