#### 5.2. Inclusion criteria

- Males and females of age 18 65 infected with *S. stercoralis (*positive by at least two Baermann assays of two different days and infection intensities of at least 0.1 LPG in the two stool samples (5g stool / Baermann assay).
- 2. Written informed consent signed by the participant him/herself. In case the person is illiterate, an impartial witness that can read and write has to sign the consent and the illiterate participant to give a thumb print.
- 3. Agree to comply with the study procedures, including to be examined by a study physician at the beginning of the study and to provide three stool samples at the beginning (baseline) and three stool samples approximately four weeks after treatment (follow-up).

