## 5.5. Concomitant therapy

All medications taken one month before and during the study period must until the last stool examination at day 28 (trial A) post treatment (follow-up) be recorded with indication, dose regimen, date and time of administration.

Medication(s)/treatment(s) permitted during the trial

- Analgesics and antipyretics are allowed to be given to the subjects in case of fever, antiemetics to prevent nausea and vomiting and/or antibiotics to prevent or treat bacterial superinfection.

Medication(s)/treatment(s) NOT permitted during the trial

- No other active drugs against helminths are permitted during the trial

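### Ivermectin re-treatment is dated day 21, before the stools that decide who needs it can be complete, and SAE reporting stops at day 21 although AE observation runs to day 28

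*Combined protocol and SAP*

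**What the plan says.** Section 4.3.4 fixes the efficacy assessment: "The efficacy of the treatment will be determined 28 days post-treatment by collecting another three stool samples". It then dates the ivermectin dose: "At the end of the study (day 21) all participants remaining positive for" *S. stercoralis* receive 200 μg/kg.

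Other places give the stool timing as follows:

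- Synopsis: "The efficacy of the treatment will be determined 21-28 days post-treatment by collecting another three stool samples". Section 4.3 gives the same range for follow-up, and Section 4.5 gives three to four weeks.
- Section 5.2: participants agree to provide "three stool samples approximately four weeks after treatment (follow-up").
- Section 5.5: concomitant medication must "until the last stool examination at day 28 (trial A) post treatment (follow-up) be recorded".
- Table 1 (Section 4.6): the only stool visit after treatment is day 28. There is no day-21 visit.

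For placebo recipients, Section 4.4 says "Participants treated with placebo will be treated at follow up (4 post treatment) with ivermectin", with the unit after the 4 missing. Section 9.6 says three to four weeks.

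On safety, Section 6.1.5 closes SAE reporting at 21 days after treatment. Section 6.1.2 runs AE observation to 28 days, and Table 1 marks SAE capture at day 28. Section 6.3 asks for any SAE to be notified within 24 hours and gives no closing day. Section 6.1.5 also has SAEs arising after the study period reported if they are considered possibly related.

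**The concern.** The dose is conditional on still being positive, and that status comes from the follow-up stools. If those are taken at day 28, nobody's status is known on day 21 and the instruction cannot be followed. If a site reconciles the two dates by starting stools on day 21 and dosing those who are positive, the remaining follow-up samples are taken under ivermectin. The dose also falls inside the 28-day AE observation period and before the day-28 AE interview, so reactions to it could be recorded against the randomised drug.

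The SAE date compounds this. Section 4.3.4 calls day 21 the end of the study. A site could therefore treat days 22 to 28 as lying after the study period, when Section 6.1.5 asks only for possibly related events. Complete SAE capture matters here because Section 5.4 puts the study on hold for any SAE and Section 11.2 sets up no data and safety monitoring board.

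**Working it through.** This is mainly a comparison of stated times. The plan has no figure of its own to reproduce on this point.

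**1. Dose against stools, as Section 4.3.4 is written.** Stools at day 28, dose at day 21: 28 − 21 = 7. The dose comes 7 days before the samples that decide who receives it.

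**2. Dose against stools, in the most generous window.** Take the first sample on day 21, the earliest day in the Synopsis. Section 4.3.1 describes the baseline collection as "three stool samples (if possible on three consecutive days or otherwise within a total maximum of 6 days"). Assume the same pattern at follow-up, which the plan does not state in so many words.

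- One sample per day: 21 + 2 = day 23 for the third.
- Spread over 6 days: 21 + 5 = day 26 for the third.

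Day 21 is therefore at least 2 days too early under any stated window, before allowing for reading the samples.

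**3. What a day-21 dose would touch.** Suppose the first sample is taken, read as positive and followed by the dose, all on day 21. No section prescribes this sequence.

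- Cure: Section 4.3.4 counts a participant as cured only if no sample contains larvae. One positive sample already makes the participant not cured, so later samples cannot change the result.
- Larvae reduction rate: the follow-up count averages three duplicate Baermann assays. 3 − 1 = 2 of the 3 samples, or 4 of the 6 assays, would follow ivermectin.
- AE interview: day 28 is 7 days after the dose.

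**4. SAE window.** Section 6.1.5 closes at day 21; Section 6.1.2 and Table 1 go to day 28. 28 − 21 = 7 days on which sites hold conflicting instructions.

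**5. How many people the dose concerns.** From Section 7.2, trial B has 350 enrolled, 10% loss to follow-up and an 89% cure rate in both arms.

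- Followed up: 350 × 0.90 = 315.
- Not cured: 315 × (1 − 0.89) = 34.65, about 35, or about 17 per arm.

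Sections 3 and 4.3 present 8 mg as the outcome of trial A, so trial A is taken as finished. If it were not, its assumed cure rates (2.5%, 30%, 55%, 75%, 85%, 90%, 95%) and 30 × 0.90 = 27 per arm would add 27 × (0.975 + 0.70 + 0.45 + 0.25 + 0.15 + 0.10 + 0.05) = 27 × 2.675, about 72 of 189. These are counts of people re-treated, not of people harmed or wrongly dosed.

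**The case against.** The best reply is that day 21 is a stray date. The dose is placed at the end of the study and limited to those still positive, a status defined by the stools described just before it. Table 1 has no day-21 visit, and other sections give day 28 or a 21-to-28-day window. A site would have to wait for results, so the error corrects itself. On SAEs, Table 1 already captures events at day 28, Section 6.1.2 observes AEs to day 28, and Section 6.3 requires notification of any SAE without an end day.

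Much of this stands. Day 21 may well be left over, or be the start of the window. But both dates sit in operative rules and no other section overrides them. Section 6.3 and the late-event clause in Section 6.1.5 cover days 22 to 28 only in part: the first gives no period, and the second is limited to possibly related events.

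A reader might infer three stronger things that the documents do not support:

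- **That rescue ivermectin biases the cure rate.** The dose is only for those already found positive, who count as not cured whatever follows. The effect on the larvae reduction rate, a secondary endpoint, needs the unwritten same-day sequence in step 3 of the working.
- **That women would be re-treated without a pregnancy check.** Section 4.3.2 describes the urine test at baseline only. However, the Table 1 footnote listing that test is attached to no visible row in the text as extracted, so a later mark cannot be excluded. The pregnancy risk set out in Section 2 concerns moxidectin; none is stated for ivermectin.
- **That the dose breaches the ban on other anthelmintics.** Section 5.5 does say "No other active drugs against helminths are permitted during the trial", but a dose that the protocol itself prescribes at study end is not clearly concomitant therapy.

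**Conclusion.** The point holds as two dates that are wrong as written. Re-treatment at day 21 comes 7 days before the stools in its own section, and at least 2 days before the third sample in the widest window. SAE reporting closes 7 days before AE observation and before the SAE capture in Table 1.

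The size is modest. The cure endpoint is not shown to be affected, no sample size or power figure changes, and the text does not show that anyone would be dosed early. What is exposed is the follow-up larvae counts, the day-28 AE interview and complete SAE capture on days 22 to 28, should a site follow the day-21 dates. The figure of about 35 people re-treated in trial B rests on the plan's 89% cure rate and 10% loss, and on trial A being finished. The day-23 figure assumes one follow-up sample per day.

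A repeat pregnancy test and AE follow-up after the ivermectin dose are not required changes on this evidence. At most they are queries to the sponsor.

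**What to change.** - **Section 4.3.4:** replace day 21 with a single time: after all three follow-up stool samples have been collected and read and the day-28 AE interview is done. Waiting for the reading matters, because collection alone does not establish who is positive.
- **Sections 4.4 and 9.6:** use the same timing for placebo recipients, completing the missing unit in Section 4.4.
- **Section 6.1.5:** run SAE reporting to day 28, or to the last follow-up visit if later, to match Section 6.1.2 and Table 1.

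The cost is a few words. Those still positive, about 35 people in trial B, wait about a week longer than under a day-21 dose. The wait is a few days more if the three samples begin on day 28 instead of ending there: with one sample per day the third falls on day 28 + 2 = 30, which is 30 − 21 = 9 days after day 21, plus reading time. Section 9.6 already regards a delay of three to four weeks as acceptable for placebo recipients; this timing would come at or slightly beyond the end of that range.
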